7. Presence of pterygium, extending beyond the limbus, with associated conjunctival hyperemia in the quadrant containing the pterygium of grade  $\geq 2$  at screening, as assessed by the central reading center based on ocular photography using a 5-point scale of 0 = none, 1 = mild, 2 = moderate, 3 = severe, and 4 = very severe, AND a conjunctival hyperemia score of  $\geq 1$  in at least 2 of the remaining quadrants of the same eye at screening (study eye). If both eyes are affected and meet the inclusion criteria, the eye with the higher overall hyperemia score will be used as the study eye. If both eyes are eligible and have the same hyperemia score, the right eye will be selected as the default study eye

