## 9 STATISTICAL CONSIDERATIONS

### 9.1 STATISTICAL HYPOTHESES

The null hypothesis is that there is no difference between AG-86893 and AG-86893 vehicle in the change from baseline to Day 28 in the overall conjunctival hyperemia score. The alternative hypothesis is that the active group is different from vehicle in the change from baseline to Day 28 in the overall conjunctival hyperemia score.

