### 9.2 SAMPLE SIZE DETERMINATION

As this is an exploratory study, an empirical sample size has been used.

Per sample size calculation using SAS Proc Power procedure, assuming the standard deviation of the mean overall hyperemia score is around 1.0, a study with 20 participants in each group (N=60)

should have at least 90% statistical power to detect a minimal difference of 1 in mean overall hyperemia scores among the three study groups at 95% confidence level.

For each of the 3 AG-86893 dose groups (vehicle, 0.1%, and 0.3%), approximately 20 participants with pterygium exhibiting conjunctival hyperemia are planned to complete the study. Therefore, a total of approximately 70 participants will be enrolled at up to 12 sites in order to achieve an estimated 60 evaluable participants after accounting for potential drop-outs. No more than a total of 70 participants will be enrolled in the study unless requested by Allgenensis.

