### 9.4 STATISTICAL ANALYSES

#### 9.4.1 GENERAL APPROACH

The database will be locked after all participants exit the study and all data clarification forms or queries have been resolved. Prior to database lock, a detailed Statistical Analysis Plan (SAP) will be finalized and approved. Final analysis and unmasking of participants' treatment code will occur after database lock.

Wherever appropriate, summary statistics will include the sample size, mean, standard deviation (SD), median, minimum, and maximum for continuous and ordinal variables, and frequency counts and percent for categorical variables. Data will be presented by treatment (0.1% AG-86893, 0.3% AG-86893, AG-86893 vehicle). Additional analyses between vehicle and active drug will be explored, the details of which will be described in the SAP. All testing will be two-sided and will be performed without adjustment for testing multiple measures.

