6.5 Efficacy Evaluation

All efficacy analyses will be based on the mITT population.

The primary statistical approach for assessment of difference among the treatment groups in change from baseline to Day 28 in conjunctival hyperemia score will be based on a mixed effect model. Significant baseline characteristics and their interaction might be included as covariant. Mean changes for each treatment group and the differences in mean changes will be estimated with the Least-Square means generated by the mixed model. Multiplicity adjustment will be conducted with Bonferroni approach.

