6.5.1 Primary Efficacy Variables

The primary endpoint is the change from baseline in overall conjunctival hyperemia score at Day 28, so, scores from Days 1 and 28 will be analyzed. The null hypothesis is that there is no difference between AG-86893 and AG-86893 vehicle in the change from baseline to Day 28 in the overall conjunctival hyperemia score. The alternative hypothesis is that the active group is different from vehicle in the change from baseline to Day 28 in the overall conjunctival hyperemia score. It was expected that the active group is at least 50% better than that of vehicle in the change of overall conjunctival hyperemia score.

To reserve the familywise error rate, the main treatment effect will be first assessed at the global level at $\alpha = 0.05$. If this is significant, then pairwise comparisons will be conducted using the Bonferroni adjustment for multiplicity between 1) 0.1% AG-86893 and AG-86893 vehicle; 2) 0.3% AG-86893 and AG-86893 vehicle; and 3) 0.1% AG-86893 and 0.3% AG-86893 for dose selection.

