APPENDIX 2 SAMPLE SAS CODE FRAGMENT

For estimation of main treatment effect:

SAS pseudo code for main treatment effect and LS mean estimation:

```
proc mixed data=xxx;  
  where mitt='Y'; *select the designated analysis population here (e.g.,  
  itt, pp);  
  class TREAT; *include other categorical covariants;  
  model CHANGE_OVERALL = TREAT/ddfm=statterth; *if any, include covariants  
  and interaction terms;  
  lsmeans TREAT/pdiff cl adjdfe=row adjust=bon;  
  (ods output statements)  
run;
```

SAS pseudo code for estimation of proportions and 95% CI, and the difference in proportions:

```
proc freq data=xxx;  
  tables VAR1 * VAR2/ alpha = 0.05 riskdiff (CL = MN);  
  * Miettinen and Nurminen inverted score test;  
  (ods statements)  
run;
```

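### SAP 6.5 does not keep treatment-by-covariate interactions out of the primary model; with a continuous, uncentred covariate the gating treatment test would be made at a covariate value of zero

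*SAP*

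**What the plan says.** Protocol 9.1 sets the hypothesis: "The null hypothesis is that there is no difference between AG-86893 and AG-86893 vehicle in the change from baseline to Day 28". SAP 6.5.1 repeats it and describes a two-step test. In its words, "the main treatment effect will be first assessed at the global level", at 0.05. Only if that test is significant do the three Bonferroni-adjusted pairwise comparisons follow (each dose against vehicle, and dose against dose). The stated purpose is to control the familywise error rate.

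SAP 6.5 adds that "Significant baseline characteristics and their interaction might be included as covariant". In Appendix 2 the printed PROC MIXED model contains treatment only, but the comment on the MODEL statement reads "if any, include covariants" and goes on to mention interaction terms. Another comment allows categorical covariates in the CLASS statement. The LSMEANS statement has no AT option.

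Neither document names the covariates, gives a selection threshold, says what the interaction is with, asks for centring, or says how the global test is formed once an interaction is present.

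**The concern.** A covariate entered without a treatment interaction leaves the treatment test meaning what Protocol 9.1 intends. A treatment-by-covariate term does not. With a continuous, uncentred covariate, the default Type 3 test of treatment becomes a test of equal intercepts, which is a comparison of arms at covariate zero.

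For the overall hyperemia score (a four-quadrant average), inclusion criterion 7 puts the lowest qualifying screening value at (2+1+1+0)/4 = 1.0. The Day 1 score is not itself subject to that criterion, but zero would still lie well away from the participants studied. For age, zero is impossible because entry starts at 18.

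At stake is whether the gate opens for the right reason. An interaction kept because it looks significant can produce a significant global treatment test when no effect exists. It can also close the gate on a real effect that grows with baseline redness.

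**Working it through.** **Inputs from the documents.** 20 evaluable per arm, SD 1.0, difference of 1 point (Protocol 9.2); 1:1:1 allocation (SAP 3.4); global alpha 0.05 (SAP 6.5.1). **Assumed, because the documents do not give them:** mean and SD of the baseline overall score, taken as means 1.5-2.5 and SDs 0.4-0.75; an inclusion threshold of p<0.05; one candidate covariate.

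**1. The plan's own figure.** Protocol 9.2 says the design "should have at least 90% statistical power to detect a minimal difference of 1 in mean overall hyperemia scores among the three study groups". For a one-way F-test, noncentrality = n × Σ(group mean − grand mean)² / SD². With true differences of 0, 1, 1 this is 20 × (4/9 + 1/9 + 1/9) = 13.33. On 2 and 57 df, power is 0.8997, so the 90% is reproduced. Equally spaced differences 0, 0.5, 1 give 20 × (0.25 + 0 + 0.25) = 10 and power 0.79.

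**2. What each step tests.** Write change = a(arm) + b(arm) × x + error. The Type 3 treatment test is a(1) = a(2) = a(3), the arm differences at x = 0. The LS means are a(arm) + b(arm) × mean of x. The two agree only if the slopes are equal or x is centred.

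**3. If the interaction is in the model regardless of the data.** The variance of an arm comparison at x = 0 is inflated by about 1 + (mean/SD)², and the noncentrality is divided by that factor (df 2 and 54). For a constant 1-point effect in both active arms:

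- Mean 2.0, SD 0.5: factor 17, noncentrality 13.33/17 = 0.78, power 0.11 (0.10 simulated).
- Mean 1.5, SD 0.7: factor 5.59, noncentrality 2.38, power 0.25.
- Mean 2.5, SD 0.5: factor 26, noncentrality 0.51, power 0.09.

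Simulation with the score held to quarter-point steps from 1 to 4, and baseline mean 1.75-2.0 with SD 0.4-0.75, gives about 10-15%. The same model with the covariate centred has power 0.899 (0.883 simulated).

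**4. If the interaction is added only when p<0.05.** This is closer to the SAP's wording. Simulated results:

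| True state | Interaction enters | Gate rejects when it enters | Gate rejects overall |
|---|---|---|---|
| No effect | about 5% | 0.68-0.81 | 0.080-0.085 |
| Constant 1-point effect, both doses | about 5% | 0.61-0.71 | 0.88-0.89 |
| Effect proportional to baseline, 1 point at the mean | 9-17% | 0.17-0.40 | 0.78-0.83 for baseline means 1.75-2.0; 0.76-0.85 over the wider range |

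One null run shows where the excess comes from. The interaction enters in 0.0504 of trials and 0.679 of those reject, which contributes 0.0504 × 0.679 = 0.034. Trials without the interaction contribute about 0.050. The total is 0.084. At an inclusion threshold of p<0.10 the rate is 0.089-0.095. If the interaction is always included, the size stays at 0.05; the inflation comes from selecting it.

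**5. Categorical covariate.** The Type 3 test then averages over levels with equal weight, so nothing is evaluated at zero. For a two-level factor and differences 0, 1, 1, power is 0.90 with a 10/10 split per arm, 0.83 with 14/6 and 0.72 with 16/4. Size is about 0.05.

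**The case against.** The strongest reply is that the trigger may never occur. Grammatically, the interaction in SAP 6.5 most naturally refers to interactions among baseline characteristics, which do not cross with treatment and leave its test alone. The printed model has treatment only. The one baseline-severity factor the SAP defines is categorical (grade 2 against above 2, SAP 3.4), and most of the demographic variables in SAP 6.3 are categorical too. The study calls itself exploratory, and naming the covariates and selection rule in advance would remove the problem. All of this stands and limits the point. It does not dispose of it, because the code comment admits interaction terms beside treatment without restriction, and age and the overall score are obvious continuous candidates.

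Two stronger readings are tempting and not supported. A reader might infer that power collapses from 90% to about 10%. That requires the interaction to be included whatever the data show, and the SAP speaks of significant terms that might be included. A reader might also infer that the gate controls every analysis. SAP 6.5.1 places only the three pairwise comparisons of the primary endpoint behind it; SAP 6.5.2 explores the other endpoints separately by the same approach.

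The false-positive harm is bounded as well. The pairwise tests are Bonferroni-adjusted and made at the covariate mean, so a wrongly opened gate does not by itself yield a dose claim. The clinical hypothesis in Protocol 4.1, that at least one concentration works, rests on those comparisons.

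**Conclusion.** The point holds as a conditional defect. The SAP permits a model in which its gating test no longer tests the null in Protocol 9.1, and nothing in the text prevents it. It requires an interaction with treatment and a continuous, uncentred covariate; other covariates and interactions among baseline characteristics do not bring it about.

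Under a p<0.05 inclusion rule with one candidate, the firmer harm is a gate type I error of about 8-9%, in a procedure meant to hold 5%. The power cost is negligible for a constant effect and modest (to about 0.78-0.83) if benefit scales with baseline. These figures rest on assumed baseline means and SDs, a residual SD of 1.0, 20 per arm, and a threshold the SAP does not state. The change is worth making before lock because it is small and settles an ambiguity in the primary analysis.

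**What to change.** In SAP 6.5, state that the primary model contains no treatment-by-covariate interaction, and that both the global 2-df treatment test and the LS means come from that model. Amend the Appendix 2 comment on the MODEL statement to match. Put any treatment-by-baseline interaction in a separate supportive model, with continuous covariates centred at the overall mean so that the treatment term refers to the average participant.

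The cost is one sentence and one code comment, made before the first database lock described in SAP 8. No new data are needed, and effect modification can still be explored.

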6.5.1 Primary Efficacy Variables

The primary endpoint is the change from baseline in overall conjunctival hyperemia score at Day 28, so, scores from Days 1 and 28 will be analyzed. The null hypothesis is that there is no difference between AG-86893 and AG-86893 vehicle in the change from baseline to Day 28 in the overall conjunctival hyperemia score. The alternative hypothesis is that the active group is different from vehicle in the change from baseline to Day 28 in the overall conjunctival hyperemia score. It was expected that the active group is at least 50% better than that of vehicle in the change of overall conjunctival hyperemia score.

To reserve the familywise error rate, the main treatment effect will be first assessed at the global level at $\alpha = 0.05$. If this is significant, then pairwise comparisons will be conducted using the Bonferroni adjustment for multiplicity between 1) 0.1% AG-86893 and AG-86893 vehicle; 2) 0.3% AG-86893 and AG-86893 vehicle; and 3) 0.1% AG-86893 and 0.3% AG-86893 for dose selection.

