6.5.2 Secondary and Exploratory Variables and Sub-Study Variables

Secondary, exploratory and exploratory sub-study numerical endpoints will be explored using the same approach as outlined for the primary efficacy analysis and might include the following:

- Change from baseline in conjunctival hyperemia score at the study quadrant at Days 28
- Change from baseline in pterygium vascularity at Days 28 and 56

- Change from baseline in pterygium vessel length at Days 28 and 56
- Change from baseline in Pterygium volume at Days 28 and 56
- IOP
- BCVA in letters read correctly
- Biomicroscopy parameters for conjunctiva, cornea, and iris. Lens status scale
- TFBUT
- Lissamine green conjunctival staining score
- Fundus
- Participant questionnaire

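### Does Bonferroni after a significant global test in SAP 6.5.1 pay for multiplicity twice and waste power?

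*SAP*

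**What the plan says.** SAP 6.5.1 sets a two-stage rule for the change in overall hyperemia score at Day 28. First: "To reserve the familywise error rate, the main treatment effect will be first assessed at the global level at" 0.05. Then: "If this is significant, then pairwise comparisons will be conducted using the Bonferroni adjustment for multiplicity between" three pairs, namely each dose against vehicle and "0.1% AG-86893 and 0.3% AG-86893 for dose selection". SAP 6.5 repeats the choice: "Multiplicity adjustment will be conducted with Bonferroni approach".

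Appendix 2 codes it as "lsmeans TREAT/pdiff cl adjdfe=row adjust=bon" after the model line "model CHANGE_OVERALL = TREAT/ddfm=statterth". There is no statement for group-specific variances, so the residual variance is pooled. The covariates are open: "Significant baseline characteristics and their interaction might be included as covariant". SAP 6.5.2 carries the method on to the other endpoints, which "will be explored using the same approach as outlined for the primary efficacy analysis".

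Protocol 9.2 gives the only planning figures: an SD of about 1.0 for the mean overall score, 20 participants per group, a difference of 1, and power of at least 90% among the three groups.

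**The concern.** With three groups, if any two of the pairwise null hypotheses are true, all three means are equal. A significant global test at 0.05 followed by each pair at 0.05 is therefore a closed test with 5% familywise error, which is the aim that SAP 6.5.1 states. Dividing 0.05 by three after the gate appears to charge for multiplicity twice.

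What would be at stake is identifying the dose. The protocol wants a dose to take forward (section 4.2). Under the SAP rule a dose that truly differs from vehicle by 1 is declared in only about 75% of trials, although the planned power is about 90%.

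**Working it through.** **Inputs.** n = 20 per group, SD 1.0 and difference 1 (Protocol 9.2); global level 0.05 and pairwise level 0.05/3 = 0.0167 (SAP 6.5.1); two-sided tests (Protocol 9.4.1); pooled variance (SAP Appendix 2). Protocol 9.2 gives the SD for the score, so applying it to the change score is an assumption.

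**1. The plan's own figure.** With one group differing by 1, the noncentrality is n × Σ(mean − grand mean)²/SD² = 20 × (1/9 + 1/9 + 4/9) = 13.33. The F test on 2 and 57 df has power 0.8997, which reproduces the protocol's 90%. It is the power of the global test only.

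**2. Power of one pair.** The noncentrality is 1/√(2/20) = 3.162. A t test on 57 df has power 0.875 at 0.05 and 0.754 at 0.0167. Bonferroni therefore sets the per-dose power at about 75%.

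**3. Familywise error of the SAP rule.** Simulation with normal data and equal SDs gives about 4.2% when all means are equal and 1.7% when one pair is equal and the third group differs by 1. The rule is valid, with error to spare.

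**4. What the alternative would gain.** The alternative is the global test at 0.05 and then pairs at 0.05, with group-specific variances and Kenward-Roger degrees of freedom (400,000 simulated trials per scenario, SD 1):

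| True means (vehicle, 0.1%, 0.3%) | Claim | SAP rule | Alternative | Gain (points) |
|---|---|---|---|---|
| 0, 0, 1 | 0.3% vs vehicle | 75.4% | 83.3% | 7.9 |
| 0, 1, 1 | 0.3% vs vehicle | 75.4% | 83.4% | 8.0 |
| 0, 1, 1 | at least one dose vs vehicle | 87.9% | 89.1% | 1.2 |
| 0, 0.5, 1 | 0.3% vs vehicle | 75.1% | 77.2% | 2.1 |
| 0, 0.5, 1 | 0.1% vs vehicle | 19.7% | 32.6% | 12.9 |
| 0, 0.5, 1 | at least one dose vs vehicle | 76.2% | 77.7% | 1.5 |

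If only 0.3% works, its gain depends on the SD: 0.2 points at SD 0.6, 1.3 at 0.7, 3.6 at 0.8 and about 9.5 at 1.2. With 23 per arm at SD 1 it is 6.7 points. A half-effect lower dose still gains at small SDs (15.8 points at SD 0.6).

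**5. What it would cost with equal SDs.** Global power falls from 90.0% to about 89.1%, because three variances are estimated instead of one. The chance of declaring a truly equal pair different rises from 1.7% to about 5%. That pair is 0.1% vs 0.3% when both doses work equally, and 0.1% vs vehicle when only 0.3% works.

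**6. What it needs.**
- *Group-specific variances.* Suppose Bonferroni is dropped but the pooled variance stays. With an assumed vehicle SD of 0.7 or 0.5 against 1.0 on active, and both doses effective, familywise error is 7.4% or 8.9%. The SAP rule has 2.9% or 3.8% in the same settings.
- *Degrees of freedom.* With group-specific variances, Satterthwaite degrees of freedom let the global test run slightly high, up to about 5.4%. Kenward-Roger holds about 5%.
- *No treatment-by-covariate interaction.* With an uncentred interaction term and strongly different assumed slopes by arm, the pooled version without Bonferroni reached 12.2%. The SAP rule stayed at or below 4.4%.

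**The case for a change.** The best case for changing the rule is that the unused error is real and the power would come without extra participants. Dose selection is a declared purpose of the trial, and the gain falls there. When only 0.3% works, the global test passes without 0.3% being declared different from vehicle in 14.6% of trials under the SAP rule and in 5.7% under the alternative. The edits are few: two of wording and three of code, before the first database lock.

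The closed-test argument and the power figures stand. The claim that the gain is free does not. About 1 point of the 8.9-point drop from 14.6% to 5.7% arises only because fewer trials pass the global test. Most of the gain comes from allowing about 5% false claims on a truly equal pair instead of 1.7%, and the dose-selection comparison can be that pair. On the protocol's hypothesis that one or more concentrations work, the gain is only 1.2 to 1.5 points when both doses have an effect; it reaches about 8 only if a single dose works.

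The edits also change the variance model, the degrees of freedom and the covariate option of the primary analysis. If they passed through to SAP 6.5.2, group-specific variances would meet coarse graded scores, where every change in an arm could be identical and that arm's variance zero. Finally, Bonferroni intervals match the SAP's tests; under the alternative, a Bonferroni interval could include zero for a pair declared different.

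**Conclusion.** No change follows. The gate plus Bonferroni holds the familywise error that the SAP sets out to protect. It also tolerates the pooled variance and open covariate terms better than the sharper rule would. The alternative is valid under stated conditions and would add about 8 points of power for a dose differing by 1 when one dose works or both work equally. With means 0, 0.5 and 1 it would add about 2 points for the top dose and 13 for the lower dose. These gains assume a change-score SD of 1.0, 20 evaluable participants per arm and normal data with equal SDs; the documents give no change-score SD. Against them stand about 1 point of global power, roughly three times as many false claims on a truly equal pair (still within 5%), and the loss of matching intervals. A sponsor could reasonably choose either rule in a study that the protocol calls exploratory. The one thing to avoid is dropping Bonferroni alone while the rest of the model stays as written.

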6.5.2 Secondary and Exploratory Variables and Sub-Study Variables

Secondary, exploratory and exploratory sub-study numerical endpoints will be explored using the same approach as outlined for the primary efficacy analysis and might include the following:

- Change from baseline in conjunctival hyperemia score at the study quadrant at Days 28
- Change from baseline in pterygium vascularity at Days 28 and 56

- Change from baseline in pterygium vessel length at Days 28 and 56
- Change from baseline in Pterygium volume at Days 28 and 56
- IOP
- BCVA in letters read correctly
- Biomicroscopy parameters for conjunctiva, cornea, and iris. Lens status scale
- TFBUT
- Lissamine green conjunctival staining score
- Fundus
- Participant questionnaire

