3.1.4 Safety and Other Measures

a) Vital Sign and Laboratory Findings

Vital signs as listed below will be performed at all visits.

- Temperature ((Celsius)
- Respiratory Rate
- Systolic Blood Pressure
- Diastolic Blood Pressure
- Heart Rate
- Height (cm)
- Weight (kg)
- Body Mass Index (kg/m²)

Blood and urine samples will be collected for lab tests at Screening, Day 28, Day 84 or Early Discontinuation, and Unscheduled visits for the following tests:

- Urinalysis
- Hematology
- Serum chemistry

b) Physical Characteristics

c) Pregnancy Testing (for child-bearing participants)

d) Electrocardiogram (ECG) Findings

ECG will be performed at Screening, Day 1, Day 28, Day 84 or Early Discontinuation, and Unscheduled visits. Findings will be recorded as Abnormal or Normal.

e) Best-corrected Visual Acuity (BCVA)

BCVA using the Early Treatment Diabetic Retinopathy Study (ETDRS) visual acuity protocol will be assessed for both eyes at all scheduled visits. The number of letters read correctly will be recorded for both eyes.

f) Intraocular Pressure (IOP)

IOP (mmHg) will be measured using Goldmann applanation tonometer for both eyes at all scheduled visits.

g) Tear Film Break-up Time (TFBUT)

TFBUT (seconds) will be performed for the study eye first, then the other eye at Day 1, Day 28, Day 56, Day 84 (only if abnormal findings on Day 56) and Early Discontinuation visits.

h) Lissamine Green Conjunctival Staining

Conjunctival staining will be performed for the study eye first, then the other eye at Day 1, Day 28, Day 56, Day 84 (only if abnormal findings on Day 56) and Early Discontinuation visits using the following grading:

- 0 = None
- 1 = Mild
- 2 = Moderate
- 3 = Severe.

i) Biomicroscopy

Slit-lamp biomicroscopy examination for both eyes will be performed at all visits for following measurements:

- Eyelids (Abnormal, Normal. If Abnormal, specify)
- Conjunctiva (0 = None, 0.5 = Trace, 1 = Mild, 2 = Moderate, and 3 = Severe)
- Cornea (0 = None, 0.5 = Trace, 1 = Mild, 2 = Moderate, and 3 = Severe)
- Iris (0 = None, 0.5 = Trace, 1 = Mild, 2 = Moderate, and 3 = Severe)
- Lens Status (Clear, Opacity, Pseudophakic, Aphakic)
If Opacity:
 - Nuclear Cataract Grade (: <1, 1, 1.5, 2, 2.5, 3, >3)
 - Posterior Subcapsular Cataract Grade (: <1, 1, 1.5, 2, 2.5, 3, >3)
 - Cortical Cataract Grade (: <1, 1, 1.5, 2, 2.5, 3, >3)

j) Ophthalmoscopy Findings

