4.7 Safety Endpoints

The Medical Dictionary for Regulatory Activities nomenclature (MedDRA V21.0 at time of SAP publication, or the current version when superseded) will be used to code AEs.

Treatment-emergent AEs are any AEs with an onset date equal to or after the date of the first dose and **within 3 days** after the last dose of the study eye drop. A pre-existing event that worsens after the first dose date is considered a treatment emergent event. Treatment-related AEs are any AEs with a relationship of unlikely related, possibly related or related to study medication, or AEs with a missing relationship.

Safety endpoints include:

- Adverse events
- Concomitant medications
- Concurrent procedures
- Vital signs
- Laboratory tests (urinalysis, hematology, and serum chemistry parameters)
- Electrocardiogram
- Best-corrected visual acuity
- Intraocular pressure using a Goldmann applanation tonometer
- Biomicroscopy
- Tear film break-up time
- Lissamine green conjunctival staining
- Ophthalmoscopy

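### SAP 6.5.2 puts the only planned between-group comparison of the numerical ocular safety variables under the primary-efficacy rules (mITT, global test, Bonferroni), which do not suit safety

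*SAP*

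**What the plan says.** SAP 6.5.2 states that secondary, exploratory and sub-study numerical "endpoints will be explored using the same approach as outlined for the primary efficacy analysis and might include the following". Besides the hyperemia and pterygium measures, the list includes IOP, "BCVA in letters read correctly", biomicroscopy with a lens scale, TFBUT, lissamine green, fundus and the questionnaire.

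The primary approach is set out in SAP 6.5, 6.5.1 and Appendix 2. It is a mixed model in the mITT population. "the main treatment effect will be first assessed at the global level at" 0.05, and "If this is significant, then pairwise comparisons will be conducted using the Bonferroni adjustment for multiplicity between" each dose and vehicle and between the two doses. The sample code requests Bonferroni-adjusted differences for all pairs.

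SAP 4.7 lists the ocular variables as safety endpoints, for example "Intraocular pressure using a Goldmann applanation tonometer", and protocol 9.4.4 does the same. SAP 6.6 bases all safety analysis on the Safety population. SAP 6.6.2 summarises TFBUT, staining, IOP, BCVA and ECG by group and visit, and counts abnormal slit-lamp and fundus findings. SAP 6.6.1 counts special-interest events by group. Section 6.6 names no test, gate, adjustment, between-group estimate or interval for these variables.

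Protocol 9.3 plans analysis of variance by dose strength for BCVA, ophthalmoscopy and IOP, without a gate or Bonferroni.

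**The concern.** Familywise error control protects a claim of benefit from being made too easily. SAP 6.5.1 introduces its gate and Bonferroni step for that purpose, on the primary efficacy hypothesis. Neither document gives a reason to carry the same protection over to IOP or visual acuity. There, the error to fear is missing a real shift, and one of the three pairs sharing the alpha is dose against dose. Safety is the first-listed objective, and protocol 2.2 describes this as the first clinical study of the topical product.

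The population also changes. SAP 5.3 requires a hyperemia evaluation at both Day 1 and Day 28 for mITT. Under protocol 7.1, stopping study drug means early exit. Protocol 7.2 then calls for the Exit visit procedures, and the schedule in protocol 1.3 has no ocular photography at that visit. Someone who stops before Day 28 because of an ocular problem may therefore have no Day 28 grade and drop out of the comparison. Finally, SAP 4.2 groups efficacy data as randomised and safety data as treated, and 6.5.2 leaves open which applies to these variables.

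**Working it through.** **Inputs.** Three arms, 1:1:1 (SAP 3.4). 20 evaluable per arm, SD 1.0, difference 1, 95% confidence level (protocol 9.2). About 70 enrolled, so 70/3 ≈ 23 per arm as an upper case. Global alpha 0.05 and three Bonferroni pairs (SAP 6.5.1). Two-sided testing (protocol 9.4.1). Assumed, because the documents give no SD for any safety variable: normal data, and true shifts of 0.5 to 1.0 SD.

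**1. The plan's own figure.** Protocol 9.2 claims at least 90% power. For a one-way F test with group means (0, 0, 1), the noncentrality is n × Σ(μi − μ̄)²/σ² = 20 × 2/3 = 13.3. With 2 and 57 degrees of freedom, the critical F is 3.16 and power is 89.97%. The figure reproduces when two group means coincide; evenly spaced means (0, 0.5, 1) give 79.3%. The check below uses the same framework.

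**2. Threshold for one dose-versus-vehicle comparison, 20 per arm.** Bonferroni level: 0.05/3 = 0.0167. Critical |t| on 57 degrees of freedom: 2.002 unadjusted, 2.467 with Bonferroni, a ratio of 1.23. Standard error of the difference: √(2/20) = 0.316 SD. Smallest observed difference that is significant: 2.002 × 0.316 = 0.63 SD, against 2.467 × 0.316 = 0.78 SD.

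**3. Power for 0.3% versus vehicle, harm at 0.3% only.** The direct test uses the noncentral t with noncentrality d/√(2/n); for d = 0.67 and n = 20 this is 0.67/0.316 = 2.12. The SAP rule (global F at 0.05, then t at 0.05/3) was simulated with at least 200,000 trials per case.

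| True shift | Per arm | Direct test at 0.05 | SAP 6.5.2 rule |
|---|---|---|---|
| 0.5 SD | 20 | 34% | 19–20% |
| 0.67 SD | 20 | 55% | 37% |
| 0.75 SD | 20 | 64–65% | 46–47% |
| 1.0 SD | 20 | 87–88% | 75% |
| 0.5 SD | 23 | 39% | 23% |
| 0.67 SD | 23 | 61% | 43% |
| 1.0 SD | 23 | 92% | 82% |

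The 20-per-arm rows are the relevant ones, because SAP 6.5 uses mITT, planned at about 20 per arm.

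**4. Gate or Bonferroni?** At 20 per arm and 0.5 SD, Bonferroni alone gives 19.7% and gate plus Bonferroni 19.5%. Across all scenarios run (harm at 0.3% only, linear, or equal at both doses), the gate blocked a Bonferroni-significant result in at most 0.5% of trials. The loss is almost entirely Bonferroni.

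**5. Price of the direct test.** With no true effect, the chance of at least one false flag across the two dose-versus-vehicle comparisons of one variable is about 9%, against about 3% under the SAP rule.

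**The case against.** A reader might infer that the trial as a whole needs stronger evidence before it can flag harm. The documents do not support that. SAP 6.6 rests the safety conclusion on adverse events and abnormal changes, including BCVA and IOP, with no p-value threshold. The special-interest events of SAP 4.7.1, among them large IOP changes, substantial acuity loss and cataract progression, are counted by group and watched by the medical monitor and the data monitoring committee. Adverse events, vital signs, laboratory tests and ECG are not in the 6.5.2 list at all.

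Other limits also stand:

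- The wording is permissive: the endpoints are to be explored, and the list is of what might be included.
- The gate is most naturally each variable's own global test, not the hyperemia result, and it costs almost nothing.
- It is tempting to say that categorical findings are forced into a least-squares-means model. The sentence is limited to numerical endpoints, and the lens item can mean the cataract grades rather than the clear/opacity/pseudophakic/aphakic field. Listing fundus there is loose drafting.
- It is tempting to call Bonferroni a breach of protocol 9.4.1: "All testing will be two-sided and will be performed without adjustment for testing multiple measures". That sentence concerns multiple measures, whereas the SAP adjusts across dose pairs within one measure, so the two can coexist.
- Error control has some use for safety, since false flags accumulate over many variables.

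None of this supplies a between-group estimate in 6.6. Any p-value the SAP provides for these variables still comes from 6.5.2, in the mITT set and with the efficacy penalty.

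**Conclusion.** The point holds for the inferential comparison of the numerical ocular safety variables and no further. For shifts of 0.5 to 1.0 SD confined to 0.3%, the SAP rule costs roughly 12 to 18 percentage points of power at 20 per arm. These figures rest on normal data and SD units. They have no clinical scale, and they fit IOP or letters read better than 0-to-3 grades. The population mismatch needs no such assumption: 6.5 says mITT and 6.6 says Safety for the same variables. How many participants that would remove cannot be known from the documents. SAP 6.2.3 does map efficacy data from a treatment-discontinuation exit to the next scheduled visit, but that helps only if a photograph was taken and that visit is Day 28. This is a worthwhile low-cost improvement, not a flaw in the trial's safety monitoring.

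**What to change.** - Take the safety variables out of SAP 6.5.2.
- In 6.6, for each numerical safety variable, report change from baseline as each dose minus vehicle with an unadjusted 95% confidence interval. Use the Safety population by treatment received, with no gate and no Bonferroni, and state that the intervals are read descriptively.
- Keep fundus and categorical lens findings as the counts of abnormal findings already planned in 6.6.2, and add risk differences for new or worsened findings. Appendix 2 already contains risk-difference code.

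The cost is SAP wording and table shells, plus the higher false-flag rate per variable shown above, which adds up over the list. No data collection changes.
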